1.0 LIST OF ABBREVIATIONS

Abbreviation	Definition
AE	Adverse event
CCC	Clinical Coordinating Center
CoC	Certificate of Confidentiality
DSC	Data and Statistics Center
DSMB	Data and Safety Monitoring Board
DHHS	Department of Health and Human Services
EDC	Electronic data capture
ERC	Ethics Review Committee
FWA	Federalwide Assurance
GCP	Good Clinical Practice
HIPAA	Health Insurance Portability and Accountability Act
ICF	Informed Consent Form
IRB	Institutional Review Board
LN	Lead Node
MDMA	Methylenedioxyamphetamine (Ecstasy)
NIDA	National Institute on Drug Abuse
NIH	National Institutes of Health
ODD	Opioid use disorder
PI	Principal Investigator
SAE	Serious adverse event
TAU	Treatment-as-usual
TLFB	Timeline Follow-Back
UDS	Urine drug screen

2.0 STUDY SYNOPSIS

2.1 Study Objectives

CTN-0051-A2 (also referred to as “ancillary study”) is an observational study intended to describe opioid use amongst opioid use disorder patients following their discharge into the community from inpatient detoxification and/or short-term residential treatment programs affiliated with CTN-0051 (referred to as “parent study”).

2.2 Study Design and Outcomes

Participant recruitment will begin after recruitment for CTN-0051 has been completed. Opioid use disorder patients will be recruited prior to leaving detoxification and/or short-term residential programs. Screening and baseline data (focused on demographics, diagnosis and service utilization) will be collected prior to discharge, and follow-up data (focused on opioid use) will be collected at weeks 1, 4 and 8 following discharge to the community. All data measures are similar to those used in CTN-0051.

2.3 Sample Size and Study Population

Participants will be a convenience sample of approximately three hundred sixty (360) opioid dependent patients leaving detoxification or short-term residential units at sites participating in CTN-0051. Approximately 60 participants will be recruited at each of approximately six sites.

Since this study utilizes a convenience sample and the objectives are to simply describe opioid use post-discharge, only detectable effect sizes were calculated (i.e., no sample size calculations performed). These effect sizes considered the evaluation of the association between post-baseline opioid use and a binary covariate such as gender, and use of medication-assisted treatment. Results of the effect size calculations are shown in Section 13.2.

[figure not shown]
2.4 Assessments and Duration

Participants will be consented prior to their discharge from the detoxification and/or short-term residential unit, screening and baseline assessments will be conducted prior to discharge, and then patients will be followed at approximately week 1, week 4 and week 8 post-discharge to the community. Assessments include: DSM-5, detoxification service utilization, post-discharge treatment plans, Timeline Follow-Back (TLFB), and urine drug screen (UDS). See Study Assessments Table, Section 11.0. Participant-level data collected in the study will not be shared with the treatment programs.

2.5 Safety Reporting

Only overdoses, whether hospitalized or not, and all deaths will be collected for this study.

3.0 STUDY SCHEMA

4.0 INTRODUCTION

4.1 Background and Significance to the Field

For opioid use disorder patients in the U.S. and most of the rest of the world, detoxification or detoxification followed by short-term residential treatment, with the goal of achieving long-term abstinence from opioid misuse is a mainstay of treatment. Although it is widely believed that many patients treated in this way will rapidly relapse to opioid misuse – leading to a costly and ineffectual cycle of readmission for repeated detoxifications – there is scant data on opioid use outcomes following discharge from these programs. Searches of PubMed, NIH Reporter, and ClinicalTrials.gov for “clinical outcomes following opioid detoxification” and the like, mostly

reveal studies focused on detoxification methods, medication schedules, withdrawal symptomatology, tolerability and the proportion of patients completing detoxification.¹⁻⁶ Three studies,⁷⁻⁹ two of them from Europe, focused on subsequent outcomes (e.g., use, misuse, relapse) after patients completed detoxification. Gossop et al⁷ followed eighty patients discharged from 21-day methadone withdrawal programs at two United Kingdom hospitals between 1984 and 1986. Seventy-one percent used opioids within the first six weeks of discharge, and 81% used opioids at some point during the six-month follow-up, though at the six-month endpoint 51% were opioid-free. Broers et al⁸ followed 73 patients discharged from a Geneva, Switzerland 15-day (average) methadone tapering program between 1994 and 1995. Sixty-five percent were using drugs again (half of them regularly) within the first four weeks. At the six-month endpoint half of the population was physically dependent again. Chutuape et al⁹ followed 113 patients discharged from a 3-day medical (mostly clonidine) detoxification program in Baltimore, Maryland between May and November 1996. At the one-, three- and six-month post-discharge assessments, 25-36% reported almost daily use, 21-30% reported no use, and the remainder reported occasional use. Overall, the mean number of days of heroin use decreased from 28 days (in the month prior to admission) to 11-14 days. In addition, several studies, most of them randomized trials of buprenorphine detoxification, collected limited datasets on post-detoxification outcomes which were disappointing (only 3-47% self-reporting abstinence, and only 7-31% producing negative urine drug screens over one- to three-month follow up periods).¹⁰⁻²⁰

The overarching goal of the CTN-0051 parent study is to foster adoption of new relapse-prevention pharmacotherapies in community-based treatment programs where these could have a substantial public health impact. CTN-0051 is an open-label randomized comparative effectiveness trial of extended-release injectable naltrexone (XR-NTX, Vivitrol®), an opioid antagonist recently approved and indicated for the prevention of relapse to opioid dependence, versus buprenorphine-naloxone (BUP-NX, Suboxone®), a high affinity partial agonist indicated for maintenance treatment of opioid dependence. Participants in the CTN-0051 parent study are recruited from detoxification and short-term residential units, randomized and inducted onto one or the other treatment, and are then discharged to the community and treated for 24 weeks and followed for an additional 3 months post-treatment. The primary outcome is the time to relapse.

A treatment-as-usual (TAU) arm was considered at the time CTN-0051 was developed, but was not pursued for reasons including added cost and that it would slow recruitment to the two arms addressing CTN-0051's primary goals. The goal of this ancillary study is to collect a minimal data set from a similar TAU group in order to describe naturalistic opioid use outcomes after discharge from these detoxification and/or short-term residential programs. This ancillary study will be carried out by existing CTN-0051 staff. Recruitment will begin once recruitment for CTN-0051 has ended, and will continue during the treatment and follow-up phases of CTN-0051.

5.0 OBJECTIVES

5.1 Primary Objective

The primary objective is to follow a group of participants with opioid use disorder to estimate treatment-as-usual rates of opioid use clinical outcomes following discharge to the community from detoxification and/or short-term residential programs.

6.0 STUDY DESIGN

6.1 Overview of Study Design

This is an observational study of participants with opioid use disorder leaving the same detoxification and/or short-term residential units from which participants for CTN-0051 are recruited, but who are discharged to TAU in the community. We will collect similar drug use measures as are collected in CTN-0051 that will allow us to estimate (1) days to first use and days to regular use, (2) number of days of use during the first four and eight weeks post-discharge to the community, and (3) number of positive, negative and missing UDSs at weeks 1, 4 and 8 post-discharge to the community.

6.2 Duration of Study and Visit Schedule

Participants will be in the study for approximately 8 weeks following discharge to the community, with visits at baseline, week 1, week 4 and week 8.

7.0 STUDY POPULATION

Approximately three hundred sixty (360) participants will be enrolled. Participants will be patients that were admitted to detoxification or short-term residential programs associated with CTN-0051 for opioid use disorder and that were discharged to the community.

7.1 Participant Inclusion Criteria

1. 18 years of age and older;
2. Meet DSM-5 criteria for opioid-use disorder (heroin or prescription opioids);
3. Have used opioids other than as specifically prescribed within thirty days prior to consent;
4. Seeking treatment for opioid dependence;
5. Able to provide written informed consent; and
6. Able to speak English sufficiently to understand the study procedures.

7.2 Participant Exclusion Criteria

1. Serious medical, psychiatric or substance use disorder that, in the opinion of the Site Principal Investigator (PI), would make participation hazardous to the participant, compromise study findings or prevent the participant from completing the study;
2. Suicidal or homicidal ideation that requires immediate attention;
3. Maintenance on methadone at doses of 30mg or greater at the time of signing consent;
4. Presence of pain of sufficient severity as to require ongoing pain management with opioids;
5. Currently in jail, prison or any inpatient overnight facility as required by court of law or have a pending legal action which may prevent an individual from completing the study;
6. If female, currently pregnant or breastfeeding or planning on conception; or
7. Prior participation in parent study CTN-0051.

7.3 Participant Recruitment

Participants will be recruited from the same detoxification and/or short-term residential programs participating in CTN-0051. Candidates admitted for opioid use disorder will be approached by research staff and provided information about the study.

8.0 SITE SELECTION

8.1 Number of Sites

Approximately six of the CTN-0051 sites will participate.

9.0 OUTCOME MEASURES

9.1 Outcome Measures

Outcomes are (1) days to first use and days to regular use (from TLFB), (2) number of days of use during the first four and eight weeks post-discharge to the community (from TLFB), and (3) number of positive, negative and missing UDSs at weeks 1, 4 and 8 (from UDS). Overdoses and deaths will also be tracked (from safety event reporting).

10.0 STUDY PROCEDURES

10.1 Informed Consent

All candidates for the study will be given a current local Institutional Review Board (IRB)-approved copy of the Informed Consent Form (ICF) to read. Appropriately qualified and trained study personnel will explain all aspects of the study and answer all of the study candidate's questions. Study procedures and the potential risks and benefits of participating in the study will be explained. Permission to access and extract information from their medical record will be obtained. After signing the consent form, participants will be given a copy of the form to keep for their records.

10.2 Screening/Baseline Visit

The screening/baseline period may encompass the time from admission to the inpatient setting until discharge to the community. Most assessments can take place at any time during this period (following completion of informed consent) with several of these assessments needing to be completed or updated not more than 48 hours prior to discharge to the community. Screening/baseline assessments include: consent, medical release of information, demographics form, locator form, detox utilization, DSM-5 checklist, information on treatment plans, urine drug screen, and Timeline Follow-Back.

10.3 Randomization

There is no randomization in this study.

10.4 Treatment/Intervention

There is no treatment or intervention in this study.

10.5 Collection of Biospecimens

A urine sample will be collected at each in-person visit and will be tested for the presence of the following drugs using a UDS dip card: opioids, oxycodone, barbiturates, benzodiazepines, cocaine, amphetamine, methamphetamine, marijuana, methadone, buprenorphine and ecstasy (MDMA). Two additional single strip tests will be performed: one for buprenorphine (BUP10) and a more sensitive test for opiates (OPI300). Samples will not be stored. Participant-level data will not be shared with the treatment program.

10.6 Premature Withdrawal of Participants

All participants will be followed for the duration of the study (CTN-0051-A2) unless they withdraw consent, die, or the investigator (site PI or LI) or sponsor decides to discontinue their enrollment for any reason. Reasons for the investigator or sponsor terminating a participant from the study may include, but are not limited to, the participant becoming a threat to self or others, lack of funding, or early termination of the study by the Data and Safety Monitoring Board (DSMB) for safety or other reasons.

10.7 Follow-up

Participants will be followed at weeks 1, 4, and 8 where the following assessments will occur:

Week 1: Timeline follow-back, UDS, update on treatment plans, update locator, protocol-defined safety event collection.

Week 4: Timeline follow-back, UDS, update on treatment plans, update locator, protocol-defined safety event collection.

Week 8: Timeline follow-back, UDS, update on treatment plans, protocol-defined safety event collection, study termination.

10.8 Blinding

This is not a blinded study.

10.9 Participant Reimbursement

Participants will receive compensation following contribution of a viable urine sample. Payments are as follows: Baseline: \$20; Week 1: \$20; Week 4: \$20; Week 8: \$50. Maximum possible compensation is \$110.

10.10 Retention Plan

Participants will be tracked for follow-up using the same methods and rigor employed in the CTN-0051 parent study. Assessments may be collected by telephone as a last resort.

11.0 STUDY ASSESSMENTS

11.1 Table of Assessments

	Screening/ Baseline	Day 0	Week 1	Week 4	Week 8
Informed consent	X				
Medical release	X				
Inclusion/exclusion	X	X ¹			
Demographics	X				
DSM-5	X				
Locator form	X	X ¹	X	X	
TLFB	X		X	X	X
UDS		X	X	X	X
Treatment plans	X	X	X	X	X
Detox utilization	X				
Safety			X	X	X
Study termination					X

¹Review/complete if last assessment done more than 48 hours prior to discharge to community and update if necessary.

11.2 General Measures

11.2.1 Inclusion/Exclusion

This form lists each inclusion and exclusion criteria to document eligibility.

11.2.2 Locator Form

A locator form is used to obtain information to assist in finding participants. This form collects the participant's current address, email address, and phone numbers. In order to facilitate locating participants if direct contact efforts are unsuccessful, addresses and phone numbers of family/friends who may know how to reach the participant are collected, as well as information such as social security number, driver's license number and other information to aid in searches of public records. This information will be collected at screening, and will be updated at the Day 0, Week 1, and Week 4 visits. No information from this form is used in data analyses nor is this information captured in the electronic data capture system (AdvantageEDC).

11.2.3 Demographics Form

The demographics form collects information about demographic characteristics of the participant, including gender, date of birth, ethnicity, race, education, employment status, and marital status. This form is completed at screening.

11.2.4 Study Termination Form

This form tracks the participant's status in the study. It is completed at the final visit, once the Week 8 follow-up visit window lapses for participants who do not complete the final follow-up, or at any other time in the event that the participant terminates from the study (withdraws consent, dies, etc.). This form is used in data analyses to address the study completion variable. This form also provides a location for the Site PI attestation of review of all study data.

11.3 Measures of Primary and Secondary Outcomes

11.3.1 Timeline Follow-back (TLFB)

The Timeline Follow-back procedure²¹ will be used to elicit the participant's self-reported use of substances at baseline and throughout study participation. At screening, this form will be used to assess substance use for the 30-day period prior to admission to the inpatient treatment program. At Week 1, the TLFB will assess the period from discharge to the community up to the date preceding the Week 1 visit (the time in detox and/or short-term residential is not captured on this assessment). At weeks 4 and 8, the TLFB will assess each day since the previous TLFB assessment.

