13.2.3 Detectable Effect Sizes

Table 1 summarizes detectable effect sizes for the two outcomes: (a) time to first opioid use, and (b) time to first regular opioid use. The detectable hazard ratios (HRs) are calculated for various values of the standard deviation of the outcome measure and the overall percent of participants who had (a) used opioids or (b) regularly used opioids during the eight week follow-up period. Total sample sizes of 280, 320 and 360 were considered. If the target sample size of 360 is reached, and 60-70% of participants use or regularly use opioids by the week 8 follow-up visit, then there will be at least 80% power to detect a HR of approximately 1.46 with a type I error rate of 5%. On the other hand if only 320 participants are enrolled, then the detectable HR is around 1.50 and for 280 participants, then the detectable HR is around 1.40-1.75.

Table 1. Detectable hazard ratios for the outcomes measures time to (a) first opioid use, and (b) first regular opioid use

Total Sample Size	Detectable Hazard Ratio	Power (%)	Proportion of Participants who Used Opioids/ Regularly Used (%)	Standard Deviation of the Number of Days to First Opioid Use/Regular Use
280	1.75	83%	60%	0.4
	1.40	82%	70%	0.5
320	1.50	81%	60%	0.5
	1.47	83%	70%	0.5
360	1.47	82%	60%	0.5
	1.45	84%	70%	0.5

Table 2 summarizes detectable effect sizes for the outcomes based on the number of days of opioid use during the eight weeks post-discharge to the community of the study. The detectable mean differences for the two-sample *t*-test are calculated for various values of the group-specific mean and standard deviations of the outcome measure. Total sample sizes of 280, 320 and 360 were considered. If participants in one group use opioids on average two weeks out of the month, then we can detect a difference of 1.5 use days with at least 80% power (assuming a type I error rate of 5%) if the target sample size of 360 is achieved. Similarly, if participants in one group use approximately three weeks out of a month, then we can detect a difference of 1.5 days. With 320 participants enrolled, a mean difference of 1.5 days can still be detected with at least 80% power, but the detectable difference increases to 2.8 days with a total sample size of 280.

Table 2. Detectable differences in means for the number of days of opioid use during the eight weeks of follow-up

Total Sample Size*	Detectable Difference** in Means (days)	Power (%)	Mean (SD) in Group 1	Mean (SD) in Group 2

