### **5.1 Days to First Opioid Use**

The days to first opioid use will be tabulated based on the data collected on the TLFB where only illicit use is recorded. The days to first opioid use will begin being assessed on Day 0 where Day 0 is defined as the day of discharge into the community. An opioid use day is defined as use of any of the opioids reported on the TLFB including Buprenorphine, Opioid analgesics, Methadone, or Heroin. The first instance of use by self-report is defined as the first opioid use day.

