### **5.2 Days to Regular Opioid Use**

The number of days to regular use will be tabulated based on the data collected on TLFB. The days to regular use will start on Day 0 where Day 0 is defined as the day of discharge into the community. An opioid use day is defined as use of any of the opioids reported on the TLFB including Buprenorphine, Opioid analgesics, Methadone, or Heroin. The first instance of seven consecutive days of use by self-report will define the participant as a regular user. The first day of the seven consecutive days is defined as the day to regular use.

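### Time to first and time to regular opioid use have no last eligible day or censoring day, so the crude Yes/No rows and user-only day summaries in SAP Tables 8-13 rest on unequal windows (minor)

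*Protocol*

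**What the plan says.** **Data collection.** Protocol 2.4 says that "patients will be followed at approximately week 1, week 4 and week 8 post-discharge to the community". Protocol 11.3.1 ties the recall period to the previous interview, not to a calendar day: "At weeks 4 and 8, the TLFB will assess each day since the previous TLFB assessment". SAP 2.1 repeats this rule. Protocol 11.2.4 shows that a Week 8 window exists, since the termination form is completed "once the Week 8 follow-up visit window lapses for participants who do not complete the final follow-up", but neither document gives its width.

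**Analysis.** SAP 5.1 gives a start, "The days to first opioid use will begin being assessed on Day 0", and an event, "The first instance of use by self-report is defined as the first opioid use day". SAP 5.2 does the same for regular use: "The first instance of seven consecutive days of use by self-report will define the participant as a regular user". Neither section names a last eligible day or a censoring day, and SAP 3.4 applies no truncation. Tables 8-13 report Yes/No counts with no window, plus mean, SD, median, minimum and maximum days among users. Figures 2-7 mark censored observations without saying when censoring occurs.

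**Intended period.** Protocol 13.2.3 speaks of participants who used or "regularly used opioids during the eight week follow-up period". That is detectable-effect text, not an analysis rule. A four- and eight-week limit is written into the outcome definition only for number of days of use.

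**The concern.** The primary objective is to estimate opioid use rates, and a rate needs a common window. Take two participants who both first use on Day 62. If one is seen on Day 56 and the other on Day 66, a programmer following the SAP codes the first No and the second Yes, and Day 62 enters the users' mean and maximum. If attendance timing differs by medication-assisted treatment, length of stay or baseline severity, part of a subgroup difference in Tables 8-13 would reflect when people were seen. Participants seen early or lost to follow-up have fewer days at risk than the nominal 56, because SAP 6.0 does not impute days after dropout for these outcomes.

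**Working it through.** **1. The plan's own figure.** The only stated results that use an eight-week use proportion are the power values in Table 1 of Protocol 13.2.3. With d = N × proportion using and two-sided 5%, power = Φ(√d × 0.5 × ln HR − 1.96).
- N = 360, 60%, HR 1.47: d = 216, power 80.8% (stated 82%).
- N = 360, 70%, HR 1.45: d = 252, power 83.9% (stated 84%).

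Both are within 2 points. This point does not dispute them; they show that 60-70% by eight weeks is the planning range.

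**2. Hazard shape from the protocol's own citation.** Protocol 4.1 cites a United Kingdom cohort of eighty patients: 71% used within six weeks and 81% within six months. For a Weibull curve, cumulative hazard H(t) = −ln(1 − F(t)).
- H(42 days) = −ln 0.29 = 1.238; H(about 182 days) = −ln 0.19 = 1.661.
- Shape k = ln(1.661/1.238) / ln(182/42) ≈ 0.20, a strongly front-loaded hazard.

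**3. Extra chance of being coded Yes when the visit is x days late.** Assume 65% use by Day 56, the middle of the 60-70% range. Then H = −ln 0.35 = 1.050 and S(t) = exp(−H × (t/56)^k). The excess is 0.35 − S(56 + x), in percentage points:

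| Days late | k = 1 (constant) | k = 0.5 | k ≈ 0.2 (cited cohort) |
|---|---|---|---|
| 7 | 4.3 | 2.2 | 0.9 |
| 14 | 8.1 | 4.1 | 1.6 |
| 28 | 14.3 | 7.4 | 3.0 |

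**4. Cohort rate.** Assume 20-40% of participants are 14 days late.
- Constant hazard: 0.2 × 8.1 = 1.6 to 0.4 × 8.1 = 3.2 points.
- k = 0.5: 0.8 to 1.6 points.
- k ≈ 0.2: 0.3 to 0.7 points, about 1-2 of 360 participants.

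For comparison, the 95% half-width for 65% of 360 is 1.96 × √(0.65 × 0.35/360) = 4.9 points.

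**5. Dropout in the other direction.** Assume 60% by Day 56, constant hazard, and 25% seen on Day 70. Use by Day 70 is 1 − 0.4^(70/56) = 68.2%.
- No dropout: crude rate 0.75 × 60 + 0.25 × 68.2 = 62.0%. A simulation gave 62.1%, with 60.1% for both the Day 56-capped crude rate and Kaplan-Meier at Day 56.
- Add 20% lost at Day 28, when use is 1 − 0.4^0.5 = 36.8%. The uncapped crude rate is 0.2 × 36.8 + 0.8 × 62.0 = 57.0%. The capped crude rate is 0.2 × 36.8 + 0.8 × 60 = 55.4%.

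The true value is 60%. With dropout, capping alone takes the crude count further below it.

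**The case against.** The best reply is that the effect is small and bounded. A Week 8 window exists and lapses; its width may be in the Manual of Operations, which is not available here. Delays of 14 or 28 days have no documentary basis. The protocol's cited cohort accrued only 10 points between six weeks and six months. All of this stands, with one caution: that cohort is small and describes any use, and the documents give no comparable figure for regular use.

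A reader might also infer that the Kaplan-Meier curves and Cox models are biased. The documents do not support that. Both methods accommodate unequal follow-up by censoring, and the Kaplan-Meier value at Day 56 is not shifted when lateness is unrelated to use. Only the tails after Day 56 rest on late attenders. Nothing in either document shows that lateness is informative.

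Nor do the days-of-use tables supply a ready-made Day 56 rule. Tables 17-19 run to Week 8 without naming a day, and SAP 5.4 states no window. Protocol 13.2.3 also describes use up to the Week 8 visit, which is anchored to the visit. This mixed wording supports stating the rule rather than leaving it to be inferred.

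**Conclusion.** The gap is real and minor. No text in either document sets a last eligible day or a censoring day for these two outcomes, so the crude Yes/No rows and users-only summaries in Tables 8-13 are not eight-week figures. Under the stated assumptions (65% by Day 56, 20-40% of participants 14 days late) late visits raise the cohort rate by about 0.3-3.2 points, with the cited cohort pointing to the low end.

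Two stronger readings do not hold. One is that the plan overstates relapse: early visits and dropout act in the opposite direction and can dominate, so the sign of the net bias is unknown. The other is a spurious subgroup gap of several points: at 14 days' delay, one subgroup entirely late and the other entirely on time would differ by 8.1 points under a constant hazard but by only 1.6 under the cited cohort's shape, and neither document suggests so extreme a split.

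**What to change.** - **SAP 5.1 and 5.2:** count events on or before Day 56 only, and censor participants without an event at the earlier of Day 56 and the last day covered by the TLFB. Apply this to Tables 8-13, Figures 2-7 and the Cox models.
- **SAP 5.2:** state how a seven-day run that starts by Day 56 but ends after it is counted. Regular use is dated to the first day of the run, so a run starting on Days 51-56 can be confirmed only with later days. Requiring all seven days by Day 56 keeps the result independent of the visit date.
- **Tables 8-13:** report the Kaplan-Meier proportion with any or regular use by Day 56, with a confidence interval, as the eight-week rate beside the crude counts. This is needed because the cap alone does not correct for early visits and dropout. It relies on censoring being unrelated to use, which the table note should say.

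The cost is a few sentences, minor programming and the loss of the few events reported after Day 56. Data collection does not change.
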